**Clinical investigation of a new nanohybrid resin composite Venus Pearl in class 2
cavities– a multi-center study**

NCT01925040

Study Protocol and Statistical Analysis Plan

Date 15.08.2013

Objective of the study

The objective of this study is to compare the performance of the composite resin Venus Pearl (a development based on the material "Venus Diamond", Heraeus Kulzer, Hanau-Germany) and the commercially available control material Filtek Supreme XTE (3M/ESPE, Seefeld-Germany- available for the study center in Germany) and its equivalent material Filtek Supreme Ultra (3M/ESPE, Seefeld-Germany- available for the study center in the United States) for the restoration of class II-cavities. Primary endpoints of the study are: loss of the restoration, fracture of the restoration, postoperative sensitivity, marginal discoloration and marginal gap or step formation. Secondary endpoints are the evaluation of secondary caries, plaque accumulation and gingival reactions.

Ethics

The study is in accordance with the declaration of Helsinki. The study protocol will be assessed and approved by the ethical committee of Hannover Medical School as well as by the Institutional Review Board of the Oregon Health and Science University (OHSU). Each patient will receive a detailed information leaflet and has to declare in writing her or his consent to participate in the study. This written informed consent can be cancelled by the patient at any time without justification.

Study design

The study will be executed as a multi-center, single-blinded and randomized clinical investigation.

Multicenter, single-blinded, and randomized clinical investigation. Study sites are the Department of conservative Dentistry, periodontology and Preventive Dentistry at the Hannover Medical School, Hannover, Germany, and the Department of Restorative Dentistry at the Oregon Health and Science University, Portland, Oregon, USA. Coordination of the study at both study sites is done by the Hannover Medical School.

General information

Time frame of the study: 2 years (with optional extension to 4 years)

Number of patients/ restorations: 90 comparable cavities per Institution (180 total), randomization

Test material: n=90 (n = 45 per site)

Control material: n=90 (n = 45 per site)

Recruitment of patients

Patients will be recruited by the Department of Conservative Dentistry, Periodontology and Preventive Dentistry of the Hannover Medical School and the Department of Restorative Dentistry of the Oregon Health and Science University (OHSU). Patients who require a class II restoration will be included in the study (see inclusion criteria). Each patient will be eligible to receive up to four restorations, with either a test or a control material. Patients will be given detailed information regarding the study before they are included in the study. Patients will receive an information leaflet and a copy of their signed informed consent form. Patients, who could not follow their examination appointments, will be contacted by phone to arrange a new appointment. Patients who miss three appointments will be classified as "drop-outs", which means that no further appointments will be scheduled for these patients regarding this study.

Inclusion criteria

- Patients should be 18 years and older.
- Study teeth should have an interproximal (Class II) carious lesion or an existing defective class II restoration requiring restorative therapy on premolars or molars.
- The maximum cavity depth determined by the radiograph will be D2 (Tyas classification).
- The teeth included in the study need to have a proximal contact with the adjacent tooth and be in occlusion with the opposing dentition.
- The teeth included in the study should be vital with no signs of pulpal pathology.
- Patients that report brushing regularly without severe gingival inflammation and/or extensive caries.
- Patients should have no allergies or systemic diseases which inhibit the treatment.
- Patients should have voluntary participation and sign a written informed consent form.
- Patients should be willing to participate in the recall/re-examination appointments.

Exclusion criteria

- Simultaneous participation in another study about dental restorative materials.
- Written informed consent form not signed.
- Nonvital pulp / periapical lesion.
- Insufficient oral hygiene despite detailed instructions.
- Pregnancy/ breast feeding before placement of the study restoration.
- Minors.
- Severe malocclusion/ malalignment/ traumatic occlusion/ bruxism.
- Known allergy to any components present in any of the materials that are used for this study.
- Unclear mucosal alterations, e.g. oral lichenoid reactions/lesions.
- Severe medical complications (organ transplants, cancer, immune-compromised, long-term antibiotic or steroid therapy).
- Infectious diseases such as HIV/Aids, Hepatitis, etc.
- Application of bleaching products less than 14 days before placement of the restoration.
- Orthodontic treatment during the study.
- Xerostomia.
- Untreated periodontal diseases.
- Rampant or extensive caries present.
- Systemic diseases with potential oral manifestation.
- Sufficient isolation according to the criteria of adhesive techniques not possible, e.g. application of rubber dam.
- Direct adhesive restoration not indicated.
- Replacement of more than one cusp indicated.
- Dental fears patients.
- Cracked tooth syndrome in study tooth.

Assessment of restorations

Restorations will be assessed by the evaluator per site at baseline (1 week after placement), as well as after 6, 12 and 24 months. Evaluations will be documented within the source data (patient's documentation) and in the Case Report Form (CRF).

Photographs of the teeth will be taken after the cavity preparation and after the restoration has been placed and finished as well as at each evaluation appointment.

If the study will be extended to 4 years, two additional assessments will be done, after 3 and 4 years (36 and 48 months) and patients will be informed of a possible request for recall at years 3 and 4 at the initiation of the study.

The evaluations will be based on the Recommendations for Conducting Controlled Clinical Studies of Dental Restorative Materials, Science Committee Project 2/98 - FDI World Dental Federation (J Adhes Dent 9 (1), 121-147 (2007)).

Partial impressions of the study teeth will be taken at baseline and during all subsequent examinations of the restorations with an addition-type silicone material (Flexitime Putty and Correct Flow, Heraeus, Hanau-Germany) and a plastic inlay tray. These impressions will be used to determine the in-vivo wear of the restorations by means of replica using a resin material (DuroCit, Struers, Willich-Germany) by means of scanning electron microscopic-warden images.

Side effects that are associated with the treatment such as local inflammation due to an inadequately placed or polished restoration, and/or oral lichenoid reactions that are in direct vicinity to the study restoration, will be documented in detail and the patient affected will be excluded from the study. In this case, the restoration will be replaced by another material as soon as possible. In addition, a restoration that fractures due to a mechanical failure of the material will also be replaced as soon as possible. It is possible to have an irreversible pulpitis develop after placement of the restoration, as often times happens during routine dental treatment. In this case, the subject will be excluded from the study and will have to continue with the appropriate treatment at the dental office of their choice at their own expense.

Biostatistical analysis

Study design

The goal of this clinical trial is to show that Venus Pearl (a development based on the material "Venus Diamond", Heraeus Kulzer, Hanau – Germany) has a better score than the commercially available control material (Filtek Supreme XTE, 3M/ESPE, Seefeld – Germany and Filtek Supreme Ultra, 3M/ESPE, USA) for the restoration of class II-cavities. Patients older than 18 who show an interproximal (Class II) carious lesion or an existing defective restoration requiring therapy on premolars or molars will be included.

For the determination of the superior outcomes of both fillings a pre-specified evaluation scheme will be used.

The assessment of the replacement will be performed at four time points (1 week, 6 months, 12 months and 24 months after replacement). For the primary analysis the score will be considered 24 months after the replacement.

The primary endpoint will be a mean score calculated as following: There are three aspects to be assessed: aesthetic, functional attribute and biological parameters. For each aspect there are respectively four categories where each has to be assessed on a scale from 1 to 5. Thereby 1 means clinically excellent, 2 means clinically good and 3 means clinically disappointing. This assessment form is given in FDI World Dental Federation (J Adhes dent 9 (1), 121 – 147 (2007)). For each

patient the points of the 12 different evaluation criteria (four categories in the three parts) will be summed up resulting in a score that ranges from 12 to 60.

Secondary endpoints are the evaluation of secondary caries, plaque accumulation and gingival reactions and the comparison of the primary score at week 1, month 6, month 12 and month 24 after restoration. Beside this, the single components of the three categories of the primary endpoints will be compared.

Randomization, stratification and blinding

This is an observer-blind clinical trial, e.g. evaluators will not know the given treatment. Restorations will be distributed evenly between the control and the experimental groups using randomization lists.

The application of the two restorative materials is limited to premolars and molars and to achieve a uniform distribution of both tooth types, stratification with the strata premolar and molar will be performed in the randomization process. In addition randomization will be stratified by center.

Randomization will be performed centrally by the Institute of Biometrics to ensure admission before allocation. The randomization will not be based on patients' names, rather than on a scheduled visit, to avoid problems with patients that do not show up for the treatment.

In order to guarantee an objective evaluation at the different time points, the Case Report Form has separate sections for each evaluation, so that the evaluators only use the form for the present examination. Through this method, the evaluator cannot see which assessment he/she gave during previous examinations. These sections will only have the patient number information.

The treatment allocation and the corresponding patient ID will be kept in a separate file that is inaccessible for operators and evaluators.

Description of the primary analysis and key secondary analysis

In the primary analysis the superiority of Venus Pearl will be investigated. Therefore the primary analysis will be conducted on the ITT population, e.g. in all randomized patients. The missing values will be replaced as described below. For the comparison of the scores of the Venus Pearl and Filtek Supreme group an ANOVA will be performed 24 months after restoration. Here, center, tooth type and treatment will be incorporated as covariables. The study is successful if the 95 % confidence interval for the treatment effect (Venus Pearl – Filtek Supreme) is below 0.

In the secondary analysis, caries (yes/no), plaque accumulation (yes/no) and BOP/ Pocket depths, will be examined with logistic regression models including center and tooth type as independent variables. Sensitivity analysis will be applied using mixed models.

If the study is extended to 4 years, the additional appointments taking place 3 and 4 years after restoration placement (late follow-up) will be evaluated descriptively using the same line as described above for the primary analysis.

Missing values

Missing values may be recorded when patients miss examination appointments. In this case the missing values will be replaced by the "last observation carried forward", where the assessment of the previous examination will be carried over to replace the missing value.

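### The plan gives two conflicting definitions of the primary endpoint (five clinical outcomes, or one 24-month score) and does not say which governs

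*Combined protocol and SAP*

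**What the plan says.** Objective of the study: "Primary endpoints of the study are: loss of the restoration, fracture of the restoration, postoperative sensitivity, marginal discoloration and marginal gap or step formation". That section mentions no score and attaches no time point, test or success rule to the five outcomes.

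Biostatistical analysis, Study design: "The primary endpoint will be a mean score calculated as following". Each of 12 criteria (four under each of the aesthetic, functional and biological aspects) is graded 1 to 5, and for each "patient the points of the 12 different evaluation criteria (four categories in the three parts) will be summed up resulting in a score" from 12 to 60. The time point is fixed: "For the primary analysis the score will be considered 24 months after the replacement". The criteria are not listed. The plan says "This assessment form is given in FDI World Dental Federation", and of the grades it describes only the first three: "Thereby 1 means clinically excellent, 2 means clinically good and 3 means clinically disappointing".

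The paragraph on secondary endpoints in the same part adds that "the single components of the three categories of the primary endpoints will be compared".

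Description of the primary analysis and key secondary analysis: the score is compared by ANOVA with center, tooth type and treatment in the model, and "The study is successful if the 95 % confidence interval for the treatment effect (Venus Pearl – Filtek Supreme) is below 0". The section refers missing values in the ITT analysis to the rule given later, which under Missing values is LOCF. Secondary models are named for caries, plaque and BOP/pocket depths only.

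**The concern.** A protocol's primary endpoint fixes what the trial may claim. Here a reader of the objective expects the result to rest on loss, fracture, sensitivity and the state of the margins. A reader of the analysis section expects it to rest on a broad sum that also has a full aesthetic aspect. A report could call either set primary and cite the same document for it.

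The two are not interchangeable. The treatment difference in a sum is the sum of the differences in its 12 criteria, so a favourable total does not imply a favourable difference on any particular criterion. Superiority could be declared under the stated rule without any shown benefit on an outcome that the objective calls primary.

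A related question, held with lower confidence, is how a failed restoration enters the 24-month score. Loss and fracture are the first two outcomes named in the objective, so a failure that drops out of the score would widen the gap between the two definitions.

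**Working it through.** **Figures in the plan.** 45 per arm per site × 2 arms × 2 sites = 180 restorations, 90 per arm. 12 criteria × 1 point = 12 and 12 × 5 points = 60. Both agree with the text. The sample size itself cannot be re-derived, because the documents give no effect size, SD, event rate or power. Nothing below depends on it being wrong.

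**The two definitions side by side.**

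| | Objective of the study | Biostatistical analysis |
|---|---|---|
| Primary endpoints | five clinical outcomes | one score |
| Time point | none given | 24 months |
| Model | none given | ANOVA (center, tooth type, treatment) |
| Success rule | none given | 95% CI for the difference below 0 |
| Individual outcomes or criteria | the five are primary | compared under secondary endpoints |
| Link between the five outcomes and the 12 criteria | none | none |
| Statement of precedence | none | none |

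The two columns cannot both be followed on what counts as meeting the primary endpoint. The wording on secondary endpoints does not settle it: it uses the plural for primary endpoints and lists the month-24 score again among the secondary comparisons.

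**Failed restorations.** Ratings are scheduled at 1 week and at 6, 12 and 24 months. Under Assessment of restorations, a fractured restoration is replaced, and patients with certain side effects or irreversible pulpitis are excluded. The primary analysis nevertheless covers all randomized patients, with missing values sent to LOCF. Two cases follow:

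- The failure is rated at the 6- or 12-month visit before replacement or exclusion. LOCF then carries the failure rating forward, and the failure counts.
- The failure occurs between visits, for example after month 12, and the restoration is replaced or the patient leaves before it is rated. If the 24-month value is treated as missing, LOCF carries the pre-failure rating forward, and the failure does not count.

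**Precision of a reported failure difference.** Inputs: 90 restorations per arm (from the plan), and an assumed failure proportion p of 5–10% in each arm (not in the documents), with restorations treated as independent. Half-width = 1.96 × √(2p(1−p)/90).

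- p = 0.05: 1.96 × √(2 × 0.05 × 0.95/90) = 0.064, or ±6.4 percentage points.
- p = 0.10: 1.96 × √(2 × 0.10 × 0.90/90) = 0.088, or ±8.8 percentage points.

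The Newcombe interval, better suited to small counts, is somewhat wider: ±7.5 points at 5/90 per arm and ±9.2 at 9/90.

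**The case against.** The strongest reply is that there is no practical doubt. Only the score has a time point, a model and a decision rule, so the analysis would be run on it. The secondary list (caries, plaque, gingival reactions) is the same in both places, which fits a reading in which the score is simply how the objective's primary list is measured. If the five outcomes are among the criteria, comparisons of them are already foreseen, although without a named model. And a win on any composite leaves its components unproven.

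Much of this stands. The score would very likely decide success, and one reconciling sentence would repair most of the defect. But no text says that the score replaces or measures the five outcomes, and the criteria are left to a form that cannot be seen here. So the documents show neither that the five are inside the score nor that they are outside it.

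Three stronger readings are tempting and should be set aside:

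- *Inflated type I error.* Five independent tests at 5% would give 1 − 0.95⁵ = 22.6%. The plan contains no such five-test analysis; it has one test.
- *A wrong sample size.* No assumptions are given for either definition, so no error can be inferred.
- *LOCF erases failures.* It would do so only for a failure never rated at a visit. The plan also defers to the FDI form, which may grade failures.

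Equally, it would be wrong to say that LOCF covers missed appointments only. The primary analysis section sends the missing values of the ITT analysis to that rule without such a limit.

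**Conclusion.** The contradiction is real and concerns a definition on which the trial's claim depends. Its size is a count: one success rule for the score, none for the five outcomes called primary in the objective, and no statement linking the two. This part is an internal inconsistency, held with high confidence; it rests on the text alone and needs no assumed SD, event rate or item mapping.

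The effect is on what may be claimed, not on error rates. A successful result would support superiority on the score and would not by itself show benefit on loss, fracture, sensitivity or the margins.

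The point about failures has lower confidence. It depends on failures going unrated before replacement or exclusion, and on LOCF being applied to them. How many restorations this would affect cannot be estimated from the documents.

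**What to change.** 1. Amend Objective of the study to name the 24-month score as the single primary endpoint. Keep the ANOVA and the 95% CI rule. Align the secondary-endpoint wording: primary endpoint in the singular, and the month-24 score not listed again as secondary.
2. List the five outcomes as named secondary endpoints with time points: loss or fracture cumulatively by 24 months, sensitivity at each scheduled visit, the marginal criteria at 24 months. Map each to a score item where the FDI form contains it. Report each arm difference with a CI that allows for several restorations per patient (the plan permits up to four). The mixed models already named for sensitivity analysis are one route.
3. State that any superiority claim refers to the score only. A multiplicity rule is needed only if the sponsor prefers to keep the five as primary.
4. For failures, state that LOCF does not supply a pre-failure rating, and that a failed restoration receives the grade the FDI form assigns to failure, by the same rule in both arms. Quote that grade in the plan, since the text describes only grades 1 to 3. Report the failure difference beside the score.

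The cost is protocol wording, an item map, one scoring rule and a few tables from assessments already planned. The downsides are a narrower headline claim and a failure difference that 90 per arm will estimate only roughly, as the working shows. The sponsor should settle all four points before unblinding.

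### The three-missed-appointments rule stops follow-up without withdrawal of consent and makes no exception for the 24-month primary examination, so LOCF must use an earlier score or has none to carry

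*Combined protocol and SAP*

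**What the plan says.** The rule stands under Recruitment of patients. It follows a sentence on re-booking: "Patients, who could not follow their examination appointments, will be contacted by phone to arrange a new appointment". The next sentence reads "Patients who miss three appointments will be classified as" drop-outs, "which means that no further appointments will be scheduled for these patients regarding this study". The trigger is a count of missed appointments. Withdrawal of consent is a separate right, described under Ethics. The text does not say whether an appointment is a scheduled examination or any booking, or whether the misses must be consecutive.

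The other parts of the plan that bear on this are:

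- **Primary time point** (Biostatistical analysis, Study design). There are four examinations: 1 week, 6, 12 and 24 months. Of these, "For the primary analysis the score will be considered 24 months after the replacement". The score is a sum over 12 criteria and is first recorded at week 1, after placement.
- **Analysis set** (Description of the primary analysis and key secondary analysis). The set is ITT, meaning everyone randomised, with missing values replaced.
- **Replacement** (Missing values). The method is LOCF: "the assessment of the previous examination will be carried over to replace the missing value". No rule covers a patient with no earlier examination.

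**The concern.** Month 24 decides the trial, and the analysis is meant to include everyone randomised. The scheduling rule nevertheless tells the sites to stop booking some patients before month 24 because of earlier non-attendance, even if they still consent and could be reached. The plan then has to fill a gap that it helped to create.

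Two things are at stake. First, a 24-month score that might have been obtained is replaced by a score from an earlier stage of the restoration's life. If the materials separate only with time, this pulls the estimated difference towards zero. Second, some randomised patients may have no score at all, and the stated ITT analysis cannot then be carried out as written. Each patient may have up to four restorations, so one lost patient can cost up to four primary values: 4/90 = 4.4% of one arm in the extreme case where all four are of the same material.

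**Working it through.** The plan states no standard deviation, target difference, power or drop-out rate, so it has no figure of its own to reproduce. The check is mainly one of logic, followed by a bounded illustration.

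**Step 1. Scheduled examinations are counted.** Only three examinations precede month 24: week 1, month 6 and month 12. Three misses before month 24 therefore have a single pattern, with all three missed. No score exists, and LOCF supplies nothing. If month 24 is itself the third miss, the rule cancels at most another attempt at that visit.

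**Step 2. Every missed booking counts, cumulatively.** The re-booking sentence just before the rule makes this reading plausible. Assume that each visit before the third miss was eventually attended:

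| Third miss falls at the visit for | Latest score held | Value LOCF gives for month 24 | 24-month examination never booked? |
|---|---|---|---|
| Week 1 | none | none | yes |
| Month 6 | week 1 | week-1 score | yes |
| Month 12 | month 6 | 6-month score | yes |
| Month 24 | month 12 | 12-month score | no; only a further re-booking is lost |

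If an earlier visit was skipped altogether, the carried score is older still.

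**Step 3. Illustration of size.** From the plan: 90 restorations per arm, and success judged by a 95% confidence interval, taken as two-sided 5%. Assumed: independent restorations, 80% power with complete data, an unchanged standard deviation, the same share *s* carried in both arms, and carried week-1 scores that show no difference between arms.

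- Difference giving 80% power: (1.960 + 0.842) × √(2/90) = 2.802 × 0.149 = 0.418 SD.
- With share *s* carried, power = Φ(2.802 × (1 − s) − 1.960).

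| s | Effect retained | Argument of Φ | Power |
|---|---|---|---|
| 0 | 100% | 0.842 | 80.0% |
| 5% | 95% | 0.702 | 75.9% |
| 10% | 90% | 0.562 | 71.3% |
| 15% | 85% | 0.422 | 66.3% |

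If the carried score already shows half of the 24-month difference, (1 − s) becomes (1 − s/2). Power is then about 78% at s = 5% and 76% at s = 10%.

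**Step 4. The part due to the rule.** The rule costs only the scores that dropped patients would still have given. If a fraction *r* of them would attend, removing the rule gives power Φ(2.802 × (1 − s(1 − r)) − 1.960). At s = 10%, where power with the rule is 71.3%:

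| r (assumed) | Power without the rule | Gain (percentage points) |
|---|---|---|
| 10% | 72.2% | 0.9 |
| 20% | 73.2% | 1.9 |
| 50% | 75.9% | 4.6 |
| 100% | 80.0% | 8.7 |

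The losses in Step 3 can be charged in full to the rule only when r = 100%.

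**The case against.** The strongest reply is that a patient who has missed three appointments despite phone contact would probably not come at month 24 either. On that view LOCF acts because of non-attendance and not because of the rule. Willingness to attend recalls is an inclusion criterion, so such patients may be few, above all if only scheduled examinations count. Mixed models are also named as a sensitivity analysis.

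Much of this stands as a limit on size. That some dropped patients could still attend is an inference, and the documents give no such share. It does not rescue the rule, which forbids even asking. The mixed models appear in the paragraph on secondary endpoints, with no stated link to missing 24-month scores, and no model recovers an examination that was never offered.

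A reader might infer three stronger conclusions that the documents do not support:

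- **That the rule will cost 4 to 14 percentage points of power.** Those are the full losses in Step 3. They require every dropped patient to be recoverable and only uninformative week-1 scores to be carried. The second condition cannot arise before month 24 if scheduled examinations are counted.
- **That the bias favours the arm with more drop-outs.** This needs drop-out unrelated to outcome and equal deterioration in both arms, and the plan supports neither. Restorations, not patients, are distributed between materials, so a patient holding both would affect both arms.
- **That the rule always discards primary data.** When the third miss is at the 24-month visit, only a further re-booking is lost.

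**Conclusion.** The concern holds in a limited form. As written, the plan can cancel the primary examination of a consenting patient. LOCF then has no score to carry (scheduled examinations counted, or a third miss at week 1), or it uses a week-1 or 6-month score (re-bookings counted). A 12-month score is the latest that can be carried, and only where the third miss falls at the 24-month visit itself. The conflict with the stated ITT set follows from the text and needs no assumption.

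The size does not follow from the text. The number affected, the share who would attend and the direction of any bias are unknown. Power of 76%, 71% or 66% is an upper bound on the harm at assumed carried shares of 5%, 10% and 15%, given the Step 3 assumptions; with few recoverable patients the cost may be under one or two percentage points. This is a change the sponsor should make because it is cheap and protects the deciding time point. It is not evidence that the trial will fail.

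**What to change.** Replace the rule with wording such as:

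> *Missed appointments, however counted, do not end follow-up. Every randomised patient who has not withdrawn consent is invited to the 24-month examination, whatever earlier visits were missed. Drop-out means withdrawal of consent, or not reached by the end of the 24-month period.*

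This works under either way of counting, so the two sites cannot apply it differently.

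Add one sentence under Missing values on how randomised patients with no post-placement score enter the ITT analysis, since LOCF cannot supply a value for them.

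Assessment of restorations separately excludes patients from the study after certain side effects. The new wording should be reconciled with that section; no view is taken here on those exclusions.

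The cost is two or three sentences and a few more calls and bookings, with no added patients or procedures.

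### Treatment-associated side effects and pulpitis end a patient's participation, and the plan does not say how an event that ends participation before it is scored enters the comparison between materials.

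*Combined protocol and SAP*

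**What the plan says.** Three parts of the combined protocol and SAP bear on this point.

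- **Exclusion.** Assessment of restorations deals with treatment-associated side effects such as "local inflammation due to an inadequately placed or polished restoration", and with lichenoid reactions close to the study restoration. These "will be documented in detail and the patient affected will be excluded from the study". The text continues: "In this case, the restoration will be replaced by another material as soon as possible". For irreversible pulpitis it says: "In this case, the subject will be excluded from the study and will have to continue with the appropriate treatment". It gives no severity threshold, does not say who judges the cause, and does not say whether the event is scored on the evaluation form before the patient leaves.
- **Outcome.** Objective of the study and the Study design part of Biostatistical analysis both state: "Secondary endpoints are the evaluation of secondary caries, plaque accumulation and gingival reactions". The analysis section adds that "caries (yes/no), plaque accumulation (yes/no) and BOP/ Pocket depths, will be examined with logistic regression models", "including center and tooth type as independent variables". Treatment is not named in that list; I read it as intended.
- **Missing data.** Missing values prescribes last observation carried forward and gives missed appointments as the reason for missing data. Exclusion for a side effect is not mentioned. The ITT population is stated for the primary analysis.

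Examinations are at 1 week and at 6, 12 and 24 months. A patient may have up to four restorations, and exclusion is of the patient, not of the restoration.

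**The concern.** A gingival reaction at a restoration can be a finding to compare between materials and also a reason for the patient to leave before the next examination. After the first week, examinations are about 6 to 12 months apart, so a reaction can appear, be judged a side effect and end participation between two of them. The last scheduled finding then predates the reaction.

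Lichenoid reactions and irreversible pulpitis raise a related issue. They lead to exclusion, but no section names either as something to be compared by material. The success rule rests only on the 24-month score. The trial could therefore meet it with no planned display of how many patients on each material left because of a tissue or pulpal event.

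**Working it through.** **Inputs from the documents.** 45 restorations per material per site at two sites: 45 × 2 = 90 per material, and 90 × 2 = 180 in total, which agrees with General information. No power, effect size, event rate or drop-out rate is given, so there is no stated figure to reproduce and the size of the effect cannot be derived.

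**What happens to an excluded reactor.** There are three possibilities.

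1. The event is scored at an examination before exclusion. Carry-forward then keeps it as present and nothing is lost.
2. The event is not scored, and last observation carried forward is applied. The patient stays in the denominator with a pre-event finding.
3. The event is not scored, and carry-forward is confined to missed appointments. The patient drops out of numerator and denominator.

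The event is lost in cases 2 and 3. The documents do not say which case applies.

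**Illustration (assumed rates).** Let p be the true 24-month reaction rate and f the share of reactors excluded unscored.

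- Case 2: observed rate = p(1 − f).
- Case 3: observed rate = p(1 − f) / (1 − p·f).

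Take p = 10% in one arm and 5% in the other, that is 9 and 4.5 of 90 restorations, a true difference of 5 points.

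| f in the 10% arm | f in the 5% arm | Case 2 rates | Difference |
|---|---|---|---|
| 0 | 0 | 10% vs 5% | 5 points |
| 0.5 | 0.5 | 5% vs 2.5% | 2.5 points |
| 1 | 1 | 0% vs 0% | 0 |
| 0.2 | 0.8 | 8% vs 1% | 7 points |
| 0.8 | 0.2 | 2% vs 4% | −2 points |

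With equal shares the difference shrinks in proportion to the share lost. With unequal shares it can widen or change sign.

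Case 3 gives nearly the same result. At f = 0.5 in both arms, 0.05/0.95 = 5.3% and 0.025/0.975 = 2.6%, a difference of 2.7 points.

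**Effect on power.** This uses a two-sided 5% normal-approximation test of two proportions with 90 per arm, treating restorations as independent. At 10% vs 5%, power is about 0.25 with every reaction counted and 0.14 with half lost, so that difference would probably be missed either way. At an assumed 20% vs 5%, power is 0.87 with every reaction counted. With half lost in each arm the rates become 10% vs 2.5% and power falls to 0.55. The loss therefore matters for the detection of large differences; for small ones the trial is too small in any case.

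**The case against.** The strongest reply has five parts.

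- **The trigger is workmanship.** The named example is inflammation from poor placement or polishing, and the endpoint is worded as gingival reactions. A reader might infer that local inflammation is itself a listed endpoint, so that the protocol contradicts itself outright. The documents do not say that. The overlap is an inference, though a close one: the example is introduced as one of a class, and no rule separates technique-related from material-related inflammation. This part of the objection stands as a limit on the wording.
- **Bleeding and pocket depth are examination findings.** A reaction found and scored at a visit is kept. That is correct, and the point is confined to events that end participation unscored.
- **Carry-forward is stated only for missed appointments.** Also correct. The alternative is that excluded patients leave the comparison, and that loses the event too.
- **Other comparisons may capture the harm.** The single components of the score are to be compared, including four biological items that the documents do not list, and postoperative sensitivity is among the primary endpoints in Objective of the study. These may capture part of it. They do not name lichenoid reactions or pulpitis, and the same uncertainty about scoring after exclusion applies to them.
- **Side effects are documented anyway.** They are, which makes the remedy cheap. But no comparison of them by material is planned.

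**Conclusion.** The point holds in conditional form. If a side effect or pulpitis ends participation before an examination scores it, the plan as written does not count it, whether earlier findings are carried forward or the patient is dropped. Keeping the patient in an ITT denominator does not repair this, because the value supplied would predate the event.

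The comparison between materials can then be biased: towards zero if similar shares of reactors are lost in both arms, and in either direction if the shares differ. The shares depend partly on a judgement of cause, so equality cannot be taken for granted.

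Two stronger readings are tempting and are not supported. One is that the more irritant material would look equally safe; full masking needs nearly all reactors in both arms to be lost unscored, or an unfavourable imbalance in the shares. The other is that these tissue events are never compared at all; the component comparison might include some of them, and the form it relies on is not reproduced in the documents.

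The size is unknown. The numbers above rest on assumed rates and shares and on independence between restorations, and they show direction only. I would ask for the change as one that should be made; it does not put the primary analysis in doubt.

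**What to change.** 1. **Count the event.** In the gingival-reaction analysis, treat as an event every gingival or local inflammatory reaction that led to replacement or exclusion, instead of carrying forward the pre-event value. State in Missing values how patients excluded for side effects or pulpitis are handled.
2. **Tabulate by assigned material, over all randomised restorations:** inflammation leading to replacement or exclusion, lichenoid reactions, irreversible pulpitis, and all exclusions with their reason. Give 95% confidence intervals that allow for up to four restorations per patient. Report zero counts with their interval too. For 0 of 90 the exact two-sided upper limit is 1 − 0.025^(1/90) = 4.0% if restorations are independent, and clustering within patients generally makes it wider.
3. **Reconcile the sections.** Assessment of restorations, Objective of the study, Biostatistical analysis and its analysis section need to agree on when inflammation is an outcome and when it ends participation. This is a request for consistency and takes no position on the clinical rule.

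The cost is SAP wording, a CRF entry for the date and reason of exclusion if none exists, and one table. Side effects are already to be documented, so no new examination is needed. The downside is that some reactions due to technique and not to the material are counted, in both arms.
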